#### **6.6.3.1 Immune-related Adverse Events (irAEs)**

The immune-modulating properties of ICIs, such as the anti-PD-1 antibody nivolumab, and anti-CTLA-4 antibody ipilimumab are able to undermine immunologic tolerance and generate a subset of AEs (called immune related AEs or irAEs) with an autoimmune inflammatory pathomechanism. IrAEs may involve every organ or tissue (Michot et al 2016). Most irAEs occur within the first 12 weeks of exposure to ICIs but some of them may appear with a delayed onset. Diagnosis of irAEs should be based on exposure to an ICI and a reasonable immune-based mechanism of the observed AE. Whenever possible, histologic examination or other immune-based diagnostic evaluations should be used to support the diagnosis. Other etiologic causes including AEs from tumor progression should be ruled out.

The spectrum of irAEs is wide and can be general or organ-specific. Examples of general irAEs in subjects treated with ICIs such as nivolumab are fatigue, fever, and chills. Organ-specific irAEs consist of pneumonitis, colitis, hepatitis, nephritis and renal dysfunction, skin adverse reactions, encephalitis, myocarditis, and endocrinopathies (hypophysitis, adrenal insufficiency, hyperglycemia).

Early recognition and management of irAEs associated with immuno-oncology agents may mitigate severe toxicity. Medical management of irAEs focuses on suppressing the immune response with non-steroidal and steroid anti-inflammatory medication. Management algorithms have been developed and should be followed for subjects with suspected irAEs. Further information on management of nivolumab/ipilimumab-associated irAEs is provided in [Section 6.6.3.2](#) and [Appendix E](#), and can also be found in the US PI.

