#### **6.6.3.2.2 Criteria for Discontinuation of Nivolumab and Ipilimumab**

If a subject meets criteria for discontinuation and the investigator is unable to determine whether the event is related to one or both checkpoint inhibitors, the subject should discontinue both nivolumab and ipilimumab with the exception of certain cases of liver function test elevation (See [Section 6.6.1](#)).

Prior to re-initiating treatment in a participant with a dosing delay lasting  $> 12$  weeks, the Medical Monitor must be consulted. Tumor assessments should continue as per protocol even if dosing is delayed. Periodic study visits to assess safety and laboratory studies should also continue as clinically indicated during such dosing delays.

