- Subjects with a Worst-Grade 4 Related TEAE
- Subjects with a Grade 5 TEAE (all deaths) at any time after first dose date and in the below categories:
  - ❖ ≤ 30 days after last dose of study treatment
  - ❖ ≤ 30 days after last dose of study treatment and not causally related to PD
  - ❖ > 30 days after last dose of study treatment
  - ❖ > 30 days after last dose of study treatment and not causally related to PD
  - ❖ ≤ 100 days after last dose of study treatment
  - ❖ ≤ 100 days after last dose of study treatment and not causally related to PD
  - ❖ > 100 days after last dose of study treatment
- Subjects with a Related Grade 5 TEAE at any time after first dose date and those in the below categories:
  - ❖ ≤ 30 days after last dose of study treatment
  - ❖ ≤ 30 days after last dose of study treatment and not causally related to PD
  - ❖ > 30 days after last dose of study treatment
  - ❖ > 30 days after last dose of study treatment and not causally related to PD
  - ❖ ≤ 100 days after last dose of study treatment
  - ❖ ≤ 100 days after last dose of study treatment and not causally related to PD
  - ❖ > 100 days after last dose of study treatment
- Subjects with a TEAE leading to dose modification (reduction or hold/delay)
- Subjects with a TEAE leading to dose reduction
- Subjects with a TEAE leading to dose hold/delay

- Subjects with TEAE leading to discontinuation:
  - Of at least one treatment component
  - Of all treatment components due to the same AE
  - Of cabozantinib/placebo
  - Of nivolumab
  - Of ipilimumab
- Subjects with Related TEAE leading to discontinuation:
  - Of at least one treatment component
  - Of all treatment components due to the same AE (note: the TEAE has to be related to all treatment components)
  - Of cabozantinib/placebo only
  - Of nivolumab only
  - Of ipilimumab only
- Subjects with TEAE leading to discontinuation and TEAE is not related to treatment and not causally related to disease under study:
  - Of at least one treatment component
  - Of all treatment components due to the same AE
  - Of cabozantinib/placebo only
  - Of nivolumab only
  - Of ipilimumab only
- Subjects with TEAE leading to discontinuation and TEAE is not related to treatment and is causally related to disease under study:
  - Of at least one treatment component
  - Of all treatment components due to the same AE (note: the TEAE has to be causally related to disease under study for all treatment components)
  - Of cabozantinib/placebo only

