Leading to Dose Reduction (applicable only for oral components)	PT (Descending Frequency of Any Grade) PT (Descending Frequency of Grade 3-4)	Worst severity: Any Grade, Grade 3-4, Grade 4, Grade 5
Leading to Dose Hold/Delay	PT (Descending Frequency of Any Grade) PT (Descending Frequency of Grade 3-4)	Worst severity: Any Grade, Grade 3-4, Grade 4, Grade 5
Leading to Dose Modification	PT (Descending Frequency of Any Grade) PT (Descending Frequency of Grade 3-4)	Worst severity: Any Grade, Grade 3-4, Grade 4, Grade 5
Leading to Treatment Discontinuation (5 summaries as shown below) 
 
• Of At Least One Component
 
• Of All Treatment Components due to The Same AE
 
	PT (Descending Frequency of Any Grade)	Worst severity: Any Grade, Grade 3-4, Grade 4, Grade 5

TEAE Included	Displays Sorted By	Format

 
• Of cab/o/placebo
 
• Of nivolumab
 
• Of ipilimumab
 
		
Leading to Treatment Discontinuation and Related to Treatment (5 summaries as shown below) 
 
• Of At Least One Component
 
• Of All Treatment Components due to The Same AE
 
• Of cab/o/placebo
 
• Of nivolumab
 
• Of ipilimumab
 
	PT (Descending Frequency of Any Grade)	Worst severity: Any Grade, Grade 3-4, Grade 4, Grade 5
Leading to Treatment Discontinuation and Not Related to Treatment (5 summaries as shown below) 
 
• Of At Least One Component
 
• Of All Treatment Components due to The Same AE
 
• Of cab/o/placebo
 
• Of nivolumab
 
• Of ipilimumab
 
	PT (Descending Frequency of Any Grade)	Worst severity: Any Grade, Grade 3-4, Grade 4, Grade 5
Leading to Treatment Discontinuation and Not Causally Related to Disease Progression (5 summaries as shown below) 
 
• Of At Least One Component
 
• Of All Treatment Components due to The Same AE
 
• Of cab/o/placebo
 
• Of nivolumab
 
• Of ipilimumab
 
	PT (Descending Frequency of Any Grade)	Worst severity: Any Grade, Grade 3-4, Grade 4, Grade 5

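### In the SAP 8.1 overall adverse event summary, the related and not-related blocks count discontinuation of each drug *only*, a different rule from the any-cause block and Table 15, so the per-drug counts are not comparable (minor)

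*SAP*

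**What the plan says.** SAP Section 8.1 lists four discontinuation blocks in the overall summary.

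- **Any cause.** Rows for at least one component, all components, and each of cabozantinib/placebo, nivolumab and ipilimumab. The single-drug rows carry no restriction.
- **Related.** Under "Subjects with Related TEAE leading to discontinuation", the single-drug rows become "Of cabozantinib/placebo only", "Of nivolumab only" and "Of ipilimumab only". The all-components row reads "Of all treatment components due to the same AE (note: the TEAE has to be related to all treatment components").
- **Not related to treatment**, in two blocks: not causally related, and causally related, to the disease under study. Both use the restricted single-drug rows.

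Table 15 plans the related discontinuations by preferred term: "Leading to Treatment Discontinuation and Related to Treatment (5 summaries as shown below"). Its rows for the oral drug, nivolumab and ipilimumab carry no restriction. The SAP neither defines *only* nor explains why the wording changes.

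The Protocol makes stopping both antibodies together an expected event. Section 6.6.3.2.2 covers a subject who meets discontinuation criteria when the investigator cannot tell which checkpoint inhibitor is responsible: "the subject should discontinue both nivolumab and ipilimumab with the exception of certain cases of liver function test elevation". Section 6.6.3.3 has both antibodies permanently stopped after a Grade 3 or 4 infusion reaction. Section 3.6.1 allows one component to continue when another stops.

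**The concern.** Adjacent rows of one safety overview appear to be built by different rules. A reader will naturally set the related nivolumab row against the any-cause nivolumab row above it and take the ratio as the treatment-related share. If the related row leaves out joint stops, that share is too low and the row will not agree with Table 15.

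The pattern left out is not far-fetched. Protocol Appendix A schedules both antibodies at Weeks 1, 4, 7 and 10, and Protocol Section 6.6.3.1 states "Most irAEs occur within the first 12 weeks of exposure to ICIs". The period when both antibodies are being given therefore largely overlaps the period when most immune-related events start. At stake is how per-drug tolerability is described in the overview. No hypothesis test depends on it.

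**Working it through.** The plan gives no figure to reproduce, so the check maps discontinuation patterns to table rows.

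**Inputs.** Three components: C (cabozantinib/placebo), N (nivolumab) and I (ipilimumab). The row definitions come from SAP Section 8.1 (any-cause and related blocks) and Table 15 (related). Assume one TEAE per subject, judged related to every component stopped, and read *only* literally. There are 2³ − 1 = 7 non-empty patterns.

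| Stopped | 8.1 any cause | 8.1 related | Table 15 related |
|---|---|---|---|
| C | at least one; C | at least one; C only | at least one; C |
| N | at least one; N | at least one; N only | at least one; N |
| I | at least one; I | at least one; I only | at least one; I |
| C+N | at least one; C; N | at least one | at least one; C; N |
| C+I | at least one; C; I | at least one | at least one; C; I |
| N+I | at least one; N; I | at least one | at least one; N; I |
| C+N+I | at least one; all; C; N; I | at least one; all | at least one; all; C; N; I |

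**Result.** All 7 patterns reach a single-drug row in the any-cause block and in Table 15. In the related block 3 of 7 do. The three two-drug patterns reach only the at-least-one row; the three-drug pattern is picked up by the all-components row.

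**A further gap.** The all-components row of the related block requires relatedness to all components. A subject who stops all three drugs for an event judged related only to the antibodies would also be left with the at-least-one row alone.

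**Other readings of *only*.**

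- *Related to that drug and no other.* Events judged related to both antibodies drop out. A joint stop attributed to nivolumab alone would still be counted under nivolumab. The set lost differs from that under the literal reading.
- *Assessed for that drug on its own.* Section 8.1 judges relatedness at regimen level unless stated otherwise, and *only* could mark that exception. Joint stops are then not excluded. Nothing in the SAP says this is meant.

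**Size.** The number affected is the number of related stops of exactly two components, plus any cases of the further gap. The documents give neither. For a given drug's related row, the undercount could be anything from zero to all related discontinuations of that drug.

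**The case against.** The strongest reply is that nothing is lost. The same subject appears in the any-cause nivolumab and ipilimumab rows of the same summary and in the Table 15 related summaries for each drug. SAP Section 5.2 also plans the primary reason for discontinuation by component, with relationship to treatment for AE stops unrelated to progression. Table 16 covers events of special interest leading to discontinuation of any infusion component, and Section 8.1 plans a listing of all AEs that led to discontinuation. Because the at-least-one row exists in both the any-cause and related blocks, the regimen-level related share can be read directly. Exclusive rows can be a legitimate display, and no formal safety comparison between arms is planned.

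Most of this stands, and it limits the point to comparability. A reader might infer that a subject who stops both antibodies appears in no single-drug row anywhere; the outputs just listed show otherwise. The reply does not make the overview rows consistent, though. The any-cause rows do not show relatedness. Table 15 is organised by preferred term and states no any-event total row; without one, adding its rows does not give a count of subjects, since one subject may have several terms. If exclusive rows are intended, the set is incomplete, because it has no two-drug rows.

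It is also fair that the Protocol does not make joint stopping the general rule. Section 6.6.3.2.2 applies when attribution is unclear, has a liver-test exception, and does not say that the oral drug continues. Other Protocol rules give patterns the rows do capture, such as stopping ipilimumab alone for Grade 3 colitis or diarrhea (Table 6-10) or all drugs for potential drug-induced liver injury (Section 6.6.1).

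**Conclusion.** The inconsistency is real and minor. The related and not-related blocks use a different, undefined rule for the single-drug rows from the any-cause block and Table 15. Under the literal reading, per-drug related counts may be understated in either arm and cannot be compared with those other outputs. This rests on the literal reading; under the third reading above, joint stops are not excluded and the fault is only unclear wording.

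No number can be attached. A reader might scale up the triplet-arm figure in Protocol Section 1.6, where 9 of 44 (20.5%) had AEs leading to discontinuation. The documents do not support that: the figure is not limited to related events, has no control-arm counterpart, and is not split by how many components were stopped. The same section has 36 of 44 still on study treatment, so 44 − 36 = 8 were off it. If both counts share a data cut, at least 9 − 8 = 1 of the nine was still receiving some treatment, but whether one or two components had stopped is not reported.

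Efficacy, alpha, power and the analysis populations are unaffected.

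**What to change.** Delete *only* from the single-component rows of the related block and both not-related blocks in SAP Section 8.1. Each row then counts every subject with a qualifying TEAE leading to discontinuation of that component, the rule already used in the any-cause block and in Table 15. All 7 patterns above then reach at least one single-drug row.

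If exclusive patterns are of interest, show them as an additional, complete set: the three single-drug patterns, the three two-drug combinations (including nivolumab with ipilimumab), and all three drugs. Define the terms in a footnote.

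The cost is SAP and table-shell wording, with no change to data collection or to any inferential analysis. Per-drug related and not-related discontinuation rates in the overview may come out higher.

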**Table 15: Adverse Event Summaries**

TEAE Included	Displays Sorted By	Format
Subject Incidence per SOC and PT by Severity		
All AEs	SOC and PT (MedDRA standard)	Worst severity: Any Grade, Grade 3-4, Grade 4, Grade 5
Events with An Incidence of $\geq 5\%$ (Any Grade) or $\geq 2\%$ (Grade 3-4) in either arm	SOC and PT (SOC per MedDRA standard, PT Within SOC by Decreasing Difference In Percent For Any Grade)	Worst severity: Any Grade, Grade 3-4, Grade 4, Grade 5
Events with An Incidence In The C+N+I Arm of $\geq 5\%$ (Any Grade) or $\geq 2\%$ (Grade 3-4) compared to control arm	SOC and PT (SOC per MedDRA standard, PT Within SOC by Decreasing Difference In Percent For Any Grade)	Worst severity: Any Grade, Grade 3-4, Grade 4, Grade 5
Subject Incidence of Non-Serious Adverse Event with An Increase of $\geq 5\%$ (Any Grade) in any arm	SOC and PT (SOC per MedDRA standard, PT Within SOC by Decreasing Difference In Percent For Any Grade)	Worst severity: Any Grade, Grade 3-4, Grade 4, Grade 5
Related AEs	SOC and PT (MedDRA standard)	Worst severity: Any Grade, Grade 3-4, Grade 4, Grade 5
SAEs	SOC and PT (MedDRA standard)	Worst severity: Any Grade, Grade 3-4, Grade 4, Grade 5
Related SAEs	SOC and PT (MedDRA standard)	Worst severity: Any Grade, Grade 3-4, Grade 4, Grade 5
Subject Incidence per PT and Severity		
All AEs	PT (Descending Freq. of Any Grade) PT (Descending Frequency of Grade 3-4) PT (Descending Freq. of Difference in Percent Between The Two Arms for Any Grades) PT (Descending Frequency of Difference in Percent Between The Two Arms for Grade3-4)	Worst severity: Any Grade, Grade 3-4, Grade 4, Grade 5
All AEs	PT (Descending Frequency of Difference in Any Grade)	Worst severity: Any Grade Odds-ratio, Relative Risk and Risk Difference
All AEs (for label)	PT (Descending Frequency of Any Grade)	Worst severity: Any Grade, Grade 1, Grade2, Grade 3, Grade 4, Grade 5
Related AEs	PT (Descending Frequency of Any Grade) PT (Descending Frequency of Grade 3-4)	Worst severity: Any Grade, Grade 3-4, Grade 4, Grade 5
SAEs	PT (Descending Frequency of Any Grade)	Worst severity: Any Grade, Grade 3-4, Grade 4, Grade 5
Related SAEs	PT (Descending Frequency of Any Grade)	Worst severity: Any Grade, Grade 3-4, Grade 4, Grade 5
Leading to Treatment Modifications and Discontinuations		
Leading to Dose Reduction (applicable only for oral components)	PT (Descending Frequency of Any Grade) PT (Descending Frequency of Grade 3-4)	Worst severity: Any Grade, Grade 3-4, Grade 4, Grade 5
Leading to Dose Hold/Delay	PT (Descending Frequency of Any Grade) PT (Descending Frequency of Grade 3-4)	Worst severity: Any Grade, Grade 3-4, Grade 4, Grade 5
Leading to Dose Modification	PT (Descending Frequency of Any Grade) PT (Descending Frequency of Grade 3-4)	Worst severity: Any Grade, Grade 3-4, Grade 4, Grade 5
Leading to Treatment Discontinuation (5 summaries as shown below) 
 
• Of At Least One Component
 
• Of All Treatment Components due to The Same AE
 
	PT (Descending Frequency of Any Grade)	Worst severity: Any Grade, Grade 3-4, Grade 4, Grade 5

TEAE Included	Displays Sorted By	Format

 
• Of cab/o/placebo
 
• Of nivolumab
 
• Of ipilimumab
 
		
Leading to Treatment Discontinuation and Related to Treatment (5 summaries as shown below) 
 
• Of At Least One Component
 
• Of All Treatment Components due to The Same AE
 
• Of cab/o/placebo
 
• Of nivolumab
 
• Of ipilimumab
 
	PT (Descending Frequency of Any Grade)	Worst severity: Any Grade, Grade 3-4, Grade 4, Grade 5
Leading to Treatment Discontinuation and Not Related to Treatment (5 summaries as shown below) 
 
• Of At Least One Component
 
• Of All Treatment Components due to The Same AE
 
• Of cab/o/placebo
 
• Of nivolumab
 
• Of ipilimumab
 
	PT (Descending Frequency of Any Grade)	Worst severity: Any Grade, Grade 3-4, Grade 4, Grade 5
Leading to Treatment Discontinuation and Not Causally Related to Disease Progression (5 summaries as shown below) 
 
• Of At Least One Component
 
• Of All Treatment Components due to The Same AE
 
• Of cab/o/placebo
 
• Of nivolumab
 
• Of ipilimumab
 
	PT (Descending Frequency of Any Grade)	Worst severity: Any Grade, Grade 3-4, Grade 4, Grade 5
Leading to Treatment Discontinuation and Causally Related to Disease Progression (5 summaries as shown below) 
 
• Of At Least One Component
 
• Of All Treatment Components due to The Same AE
 
• Of cab/o/placebo
 
• Of nivolumab
 
• Of ipilimumab
 
	PT (Descending Frequency of Any Grade)	Worst severity: Any Grade, Grade 3-4, Grade 4, Grade 5
Grade 5 AEs		
Gr 5 AEs <= 30 days After The Last Dose of Study Treatment	PT (Descending Frequency of Grade 5)	Grade 5, Odds Ratio, Relative Risk, Risk Difference
Gr 5 AEs <= 30 Days After The Last Dose of Study Treatment and Judged Not To Be Causally Related to PD	PT (Descending Frequency of Grade 5)	Grade 5, Odds Ratio, Relative Risk, Risk Difference
Gr 5 AEs <= 100 days After The Last Dose of Study Treatment	PT (Descending Frequency of Grade 5)	Grade 5, Odds Ratio, Relative Risk, Risk Difference
Gr 5 AEs <= 100 Days After The Last Dose of Study Treatment and Judged Not To Be Causally Related to PD	PT (Descending Frequency of Grade 5)	Grade 5, Odds Ratio, Relative Risk, Risk Difference
Gr 5 AEs Related to Study Treatment At Any Time	PT (Descending Frequency of Grade 5)	Grade 5, Odds Ratio, Relative Risk, Risk Difference

TEAE Included	Displays Sorted By	Format
Gr 5 AEs Related to Study Treatment and <=30 Days After The Last Dose of Study Treatment	PT (Descending Frequency of Grade 5)	Grade 5, Odds Ratio, Relative Risk, Risk Difference
Gr 5 AEs Related to Study Treatment and <=100 Days After The Last Dose of Study Treatment	PT (Descending Frequency of Grade 5)	Grade 5, Odds Ratio, Relative Risk, Risk Difference

The following data listings will also be provided with indicators for grade, relationship, seriousness, dose day of the event start/stop, days since last dose, actions taken with study treatment:

- All AEs
- Serious AEs other than Gr 5 AEs
- All AEs that led to treatment discontinuation
- All AESIs

